6.2.1.1.2 Trametinib

Based on *in vitro* and *in vivo* data, trametinib is unlikely to significantly affect the pharmacokinetics of other medicinal products via interactions with CYP enzymes or transporters.

6.2.2 Prohibited medication

The following medications or non-drug therapies are prohibited while on treatment in this study:

- Other anti-cancer therapies
- Other investigational drugs

Although not contraindicated/prohibited, certain medications drugs should be used with caution due to potential drug-drug interactions (see [Section 6.2.1.1.1](#)).

6.3 Subject numbering, treatment assignment, randomization

6.3.1 Subject numbering

Each subject is identified in the study by a Subject Number (Subject No.), that is assigned when the subjects is first enrolled for screening and is retained as the primary identifier for the subject throughout his/her entire participation in the trial. The Subject No. consists of the Center Number (Center No.) (as assigned by Novartis to the investigative site) with a sequential subject number suffixed to it, so that each subject is numbered uniquely across the entire database. Upon signing the informed consent form, the subject is assigned to the next sequential Subject No. available.

6.3.2 Treatment assignment, randomization

No randomization will be performed in this study. The assignment of a subject to enter the study will be coordinated by the sponsor.

6.4 Treatment blinding

Not applicable

6.5 Dose modification

Guidelines on management of common dabrafenib or trametinib associated toxicities and dose modification instructions are provided in [Section 6.5.1](#).

6.5.1 Dose modifications

The starting dose for subjects enrolled in the trial is set at 150 mg dabrafenib BID and 2 mg trametinib QD. Please refer to [Section 4.2](#) for more details on the dose rationale.

6.5.1.1 Mandatory dose modification and recommended clinical management for pyrexia suspected to be related to dabrafenib and/or trametinib treatment

For the purpose of this study, pyrexia is defined as fever occurring while on study treatment ($\geq 38^{\circ}\text{C}$) and pyrexia syndrome is defined as one or more of the following symptoms: chills/rigors/night sweats; flu-like symptoms. The incidence and severity of pyrexia are increased when dabrafenib is used in combination with trametinib compared to dabrafenib monotherapy. In a minority of cases the pyrexia was accompanied by symptoms such as severe rigors/chills, dehydration, hypotension, dizziness or weakness and required hospitalization.

Dabrafenib **and** trametinib must be interrupted promptly at the onset of pyrexia and should be restarted upon the improvement of symptoms at the same dose if symptom-free (temperature $< 38^{\circ}\text{C}$) for at least 24 hours.

If a subject's dose of dabrafenib and trametinib has been reduced as per the dose modification guideline, re-escalation of the subject's dose is recommended provided the following criteria are met:

- a period of 4 weeks of treatment has elapsed since treatment is restarted at the lower dose level and there is no recurrence of the AE
- the subject is deriving clinical benefit

Subjects should be comprehensively educated and receive written guidance regarding febrile episodes before starting study drug treatment and also be instructed on the importance of immediately reporting febrile episodes or pyrexia syndrome.

Subjects should be instructed to take non-steroidal anti-inflammatory drugs (NSAID) and/or paracetamol and/or metamizole, as appropriate, to control pyrexia syndrome (i.e. symptoms without documented temperature $\geq 38^{\circ}\text{C}$ degrees)

In the event of a fever ($\geq 38^{\circ}\text{C}$).

- The subject should immediately stop both dabrafenib and trametinib
- The subject should be instructed to take non-steroidal anti-pyretics, as appropriate, to control fever.
- The use of oral corticosteroids should be considered to:
 - manage acute pyrexia refractory to dose interruption and anti-pyretics (paracetamol, NSAIDs)
 - prevent further episodes of pyrexia in those with recurrent pyrexia events i.e. prophylaxis
 - In subjects experiencing pyrexia higher than 40°C (104°F), and/or pyrexia associated with rigors, severe chills, dehydration or hypotension, serum creatinine and other evidence of renal function should be monitored frequently. The frequency of monitoring must be adapted based on the individual clinical presentation.
 - Clinical evaluation for infection and hypersensitivity is recommended for subjects experiencing pyrexia not resolving within 24 hours

Dabrafenib and trametinib can be interrupted in the presence of the pyrexia syndrome (i.e. chills or rigors or night sweats or flu-like symptoms without documented temperature $\geq 38^{\circ}\text{C}$ degrees) at investigators discretion for recurrent pyrexia and should be restarted upon improvement of symptoms at the same dose if symptom free for at least 24 hours.

If recurrent pyrexia cannot be managed with dabrafenib and trametinib interruption or prophylactic steroids, dose reduce as per [Table 6-5](#).

Pyrexia accompanied by hypotension, dehydration requiring intravenous fluids, renal insufficiency and/or severe (\geq Grade 3) rigors/chills in the absence of an obvious infectious cause should be reported as a SAE.

Guidelines for dose modification and management for pyrexia considered to be related to dabrafenib and/or trametinib are provided in [Table 6-4](#).

Table 6-4 Mandatory dose modification and recommended clinical management for pyrexia suspected to be related to dabrafenib and/or trametinib treatment

Pyrexia (≥ 38°C)		
Occurrence	Recommended adverse event management guidelines	Mandatory dose modification requirements
1 st occurrence and subsequent occurrences	
 Educate subject about pyrexia and its associated syndrome (chills or rigors or night sweats or flue like symptoms) to ensure prompt recognition and reporting Clinical evaluation for infection and hypersensitivity ^b Laboratory work-up ^b Prompt administration of anti-pyretic treatment with non-steroidal anti-inflammatory drugs (NSAID) and/or paracetamol and/or metamizole at the onset of pyrexia ^a or of pyrexia syndrome Recommend oral corticosteroids (i.e., prednisone 10 mg/d) for at least 5 days or as clinically indicated^c Optimize oral corticosteroid dose as clinically indicated for pyrexia that cannot be managed with dose interruptions^c Oral hydration should be encouraged in subjects without evidence of dehydration. Intravenous hydration is recommended in subjects experiencing pyrexia complicated by dehydration/hypotension. 	
 Dabrafenib and trametinib must be interrupted promptly at the very first observation of pyrexia and should be restarted upon resolution of pyrexia (temperature < 38°C) at the same dose if pyrexia free at least 24 hours*. If recurrent pyrexia cannot be managed with interruption or prophylactic steroids, dose reduce as per Table 6-5. Re-escalation of the subject's dose is recommended if criteria in Section 6.5.1.2 are met. Note: proactive intermittent dosing is not allowed.

* Dabrafenib and Trametinib can be interrupted in the presence of pyrexia syndrome (i.e. symptoms without documented temperature ≥ 38°C degrees) at investigator discretion for recurrent pyrexia.

^a Anti-pyretic treatment should be started immediately at the onset of pyrexia or pyrexia syndrome, and prophylactic anti-pyretic treatment is recommended. Anti-pyretic treatment may include acetaminophen, ibuprofen, metamizole, or suitable anti-pyretic medication according to institutional standards. Prophylactic anti-pyretic treatment is recommended to be discontinued after three days in the absence of pyrexia.

^b For subjects experiencing pyrexia not resolving within 24 hours, if clinically indicated by the treating physician, a clinical evaluation and laboratory work-up, thorough clinical examination for signs and symptoms of infection or hypersensitivity may be performed. Laboratory work-up may include full-blood-count, electrolytes, creatinine, blood urea nitrogen (BUN), C-reactive protein (CRP), liver-function tests, blood culture, and urine culture.

^c Corticosteroids are recommended for recurrent pyrexia that cannot be managed with dose interruptions and anti-pyretic treatments and for pyrexia associated with complications. This recommendation may be superseded by local institutional guidelines where available, or the investigator's discretion on how to best manage a given subject.

6.5.1.2 Other dose modifications and reductions

The following sections address the specific instructions for mandatory dose modifications and recommended management for AEs considered suspected to be related to study treatment. For subjects who do not tolerate the protocol-specified dosing schedule, dose interruptions or modifications are mandated in order to allow subjects to continue study treatment.

Three dose reductions for dabrafenib and two dose reductions for trametinib are permitted. If more dose reductions of dabrafenib and trametinib are required, the subject must be permanently discontinued from that specific study treatment. Dose modification steps for dabrafenib and trametinib in [Table 6-5](#) must be followed for the AEs presented in [Section 6.5.1](#).

Table 6-6 provides sections where detailed dose modification and management requirements for relevant AEs can be found. All AEs are to be graded according to NCI-CTCAE v4.03, unless otherwise specified. Investigators should refer to the current dabrafenib and trametinib local prescribing information for additional information regarding the background of each drug and the management of other AEs or potential safety-related issues not specifically mentioned in this protocol.

If treatment-related toxicities occur that are specific to combination treatment of dabrafenib and trametinib, then both treatments should be simultaneously dose reduced, interrupted or discontinued with the exceptions shown below:

Exception where dose modification is necessary for **only dabrafenib**:

- Uveitis (Table 6-18)

Exception where dose modifications are necessary for **only trametinib**:

- RVO (Table 6-18) and retinal pigment epithelial detachment (RPED) (Table 6-19)
- Left ventricular ejection fraction (LVEF) reduction (Table 6-15)

If a subject's dose of dabrafenib and trametinib has been reduced per the dose modification instructions, re-escalation of the subject's dose is recommended provided the following criteria are met:

- a period of 4 weeks of treatment has passed since restarting dosing at the lower dose level and there is no recurrence of the AE
- the subject is deriving clinical benefit

For dabrafenib and/or trametinib related adverse events: if following an interruption of dabrafenib and trametinib, an AE doesn't recover to \leq Grade 1 or baseline within 4 weeks, dabrafenib and trametinib must be discontinued.

For study treatment interruptions due to adverse events unrelated to dabrafenib and/or trametinib, approval from Novartis Medical Monitor is required to restart study treatment after \geq 28 days interruption.

Table 6-5 Dose modification steps for dabrafenib and trametinib

Dose reduction for dabrafenib^{a, b}				
	Starting dose level	Dose level - 1	Dose level - 2	Dose level - 3
Dabrafenib	150 mg BID (300 mg/day)	100 mg BID (200 mg/day)	75 mg BID (150 mg/day)	50 mg BID (100 mg/day)
Dose reduction for trametinib^{a, b}				
	Starting dose level	Dose level - 1	Dose level - 2	Dose level - 3
Trametinib	2 mg QD	1.5 mg QD	1.0 mg QD	-

BID: twice daily; QD: once daily

^a. Dose modification should be based on the worst toxicity demonstrated at the last dose.

^b. Dose reduction below 50 mg BID for dabrafenib and 1.0 mg QD for trametinib are not allowed.

6.5.1.3 Dose modification and management guideline for adverse events common to dabrafenib and trametinib

Adverse events that have been reported with dabrafenib in combination with trametinib in the adjuvant melanoma setting include, but are not limited to pyrexia, fatigue, nausea, headache, chills, diarrhea, vomiting, arthralgia, and rash. The most common adverse events for dabrafenib

and trametinib combination therapy include pyrexia, fatigue, nausea, headache, chills, diarrhea, rash, arthralgia, hypertension, vomiting, and cough.

Table 6-6 Reference of AEs and toxicity management guidelines

Adverse Events	dabrafenib	trametinib	Guideline
Pyrexia	X	X	Section 6.5.1.1 Table 6-4
Abnormal liver enzyme test	X	X	Section 6.5.1.3.2 Table 6-7
Renal Function Alterations	X	X	Section 6.5.1.3.3 Table 6-8
Skin rash	X	X	Section 6.5.1.3.4 Table 6-9
Serious skin reaction	X	X	Section 6.5.1.3.5
Pneumonitis	X	X	Section 6.5.1.3.6 Table 6-10
Hand foot skin reaction	X	X	Section 6.5.1.3.8 Table 6-12
Hematologic adverse events	X	X	Section 6.5.1.3.9 Table 6-13
Non-hematologic adverse events	X	X	Section 6.5.1.3.10 Table 6-14
LVEF	X	X	Section 6.5.1.3.11 Table 6-15
Hypertension	X	X	Section 6.5.1.3.12 Table 6-16
Diarrhea/colitis	X	X	Section 6.5.1.3.13 Table 6-17
New malignancies	X	X	Section 6.5.1.3.14
Visual changes	X (Uveitis)	X (RVO)	Section 6.5.1.3.15 Table 6-18 , Table 6-19
RPED		X	Section 6.5.1.3.15 Table 6-19
Hyperglycemia	X		Section 6.5.1.3.16
Hemorrhage	X	X	Section 6.5.1.3.17
Thromboembolic events		X	Section 6.5.1.3.18
General	X	X	Section 6.5.1.3.7 Table 6-11
"X" indicates study treatment (s) that may need to be modified			

6.5.1.3.1 Guidance for corticosteroids tapering for management of adverse events common to dabrafenib and trametinib

Reduce prednisone dose by 2.5 to 5.0 mg decrements every 3–7 days until physiologic dose (5 to 7.5 mg of prednisone per day) is reached. Consider completing tapering over a period of at least 4 weeks. Slower tapering of corticosteroids therapy may be recommended if the adverse event is not showing improvement.

6.5.1.3.2 Mandatory dose modifications and recommended clinical management guidelines for abnormal liver enzyme test

Guidelines for dose modification and management of abnormal liver enzyme functions considered to be related to study treatment by the investigator are provided in [Table 6-7](#).

In addition to the instructions below, subjects with normal baseline transaminases and bilirubin who experience sudden elevations even within Grade 1, should be monitored more closely.

Table 6-7 Mandatory dose modifications and recommended clinical management guidelines for abnormal liver enzyme test

Abnormal liver enzyme tests/hepatitis		
Grade	Recommended adverse event management guidelines	Mandatory dose modification requirements
Grade 2: AST or ALT >3× ULN to ≤ 5× ULN and/or bilirubin > 1.5× ULN to ≤ 3× ULN	
 Monitor hepatic laboratory tests more frequently (every 2-3 days) until returned to baseline values 	
 Interrupt, dabrafenib and trametinib until ≤ Grade 1, and then reinstate, dabrafenib and trametinib at the same dose level.
Grade 3 or 4: AST or ALT > 5× ULN and/or bilirubin > 3× ULN	
 Monitor hepatic laboratory tests more frequently (every 2-3 days) until return to baseline values. Consider appropriate consultation* with hepatologist and liver biopsy to establish etiology of hepatic injury, if necessary If after 2-3 days new liver assessment shows worsening of laboratory test consider to initiate treatment with high dose steroids (1 to 2 mg/kg/day prednisone or equivalents) Add prophylactic antibiotics for opportunistic infections Start steroid taper as outlined in Section 6.5.1.3.1 if symptoms improve to Grade ≤1 If serum transaminase levels do not decrease 48 hours after initiation of systemic steroids, oral mycophenolate mofetil 500 mg every 12 hours may be given. Infliximab is not recommended due to its potential for hepatotoxicity 	
1st occurrence
 
 Interrupt dabrafenib and trametinib until recovery to ≤ Grade 1 or baseline 
 Reduce dabrafenib and trametinib to the next lower dose level per Table 6-5. Re-escalation of the subject's dose is recommended if criteria in Section 6.5.1.2 are met If no recovery to ≤ Grade 1 within 4 weeks, permanently discontinue dabrafenib and trametinib. 
2nd occurrence
 
 Interrupt dabrafenib and trametinib until ≤ Grade 1. 
 Reduce dabrafenib and trametinib to the next lower dose level per Table 6-5. Re-escalation of the subject's dose is recommended if criteria in Section 6.5.1.2 are met dose 
3rd occurrence
 
 Permanently discontinue dabrafenib and trametinib

*Rule out viral hepatitis and other potential causes of liver injury

Note: For additional information on follow-up of potential drug induced liver injury cases, refer to [Section 6.5.2](#).

6.5.1.3.3 Mandatory dose modifications and recommended clinical management guidelines for renal function alterations

Cases of renal insufficiency have occurred in adult patients receiving dabrafenib and the combination of dabrafenib and trametinib. Prior to start of study treatment, concomitant medications must be reviewed for the potential risk of inducing nephrotoxicity and concomitant medications may be modified if clinically possible.

Guidelines regarding management and dose reduction for renal insufficiency considered to be related to study treatment by the investigator are provided in [Table 6-8](#).

Table 6-8 Mandatory dose modifications and recommended clinical management guidelines for renal function alterations

NCI-CTCAE v4.03 for acute kidney injury

Grade	Recommended adverse event management guidelines	Mandatory dose modification requirements
Grade 1 (Creatinine level increase of >0.3 mg/dL; creatinine 1.5 - 2.0 x above baseline)	
Repeat serum creatinine within 24 hours for any increase in serum creatinine >0.5 mg/dl
 
 • If the increase in creatinine is confirmed: 
 a) Assess fluid status and consider fluid bolus b) Monitor serum creatinine at least every 2 days until back to baseline • If creatinine returns to baseline: 
 a) resume routine creatinine monitoring per protocol • Promote hydration and cessation of nephrotoxic drugs. 	
 • If the increase in creatinine is confirmed: 
 a) Interrupt treatment • If creatinine returns to baseline: 
 a) Continue dabrafenib and trametinib at the same dose.
Grade 2: (Creatinine 2 - 3 x above baseline)	
 • Closely monitor creatinine • Consult with specialist and consider renal biopsy • Promote hydration and cessation of nephrotoxic drugs. 	
1st occurrence:
 
 • Interrupt dabrafenib and trametinib until \leq Grade 1 or baseline and then reinstate dabrafenib and trametinib at the same dose. 
2nd occurrence:
 
 • Interrupt dabrafenib and trametinib until \leq Grade 1 or baseline. Once recovered, reduce dabrafenib and trametinib to the next dose level. Re-escalation of the subject's dose is recommended if criteria in Section 6.5.1.2 are met. 
3rd occurrence:
 
 • Interrupt dabrafenib and trametinib until \leq Grade 1 or baseline. Once recovered, reduce dabrafenib and trametinib to the next dose level. Re-escalation of the subject's dose is recommended if criteria in Section 6.5.1.2 are met. 
4th occurrence
 
 • Permanently discontinue dabrafenib and trametinib.

NCI-CTCAE v4.03 for acute kidney injury

Grade	Recommended adverse event management guidelines	Mandatory dose modification requirements
Grade 3 (Creatinine > 3.0 x baseline or >4.0 mg/dL; hospitalization indicated)	
 Hospitalization is indicated with frequent creatinine monitoring Consult with nephrologist. Promote hydration and cessation of nephrotoxic drugs. 	
1st occurrence:
 
 Interrupt dabrafenib and trametinib until \leq Grade 1 or baseline and then reduce dabrafenib and trametinib to the next lower dose. Re-escalation of the subject's dose is recommended if criteria in Section 6.5.1.2 are met. 
2nd occurrence:
 
 Interrupt dabrafenib and trametinib until \leq Grade 1 or baseline and then reduce dabrafenib and trametinib to the next lower dose. Re-escalation of the subject's dose is recommended if criteria in Section 6.5.1.2 are met. 
3rd occurrence:
 
 Interrupt dabrafenib and trametinib until \leq Grade 1 or baseline and then reduce dabrafenib and trametinib to the next lower dose, if available as dose level -2. If already at dose level -2 at time of occurrence, permanently discontinue dabrafenib and trametinib. Re-escalation of the subject's dose is recommended if criteria in Section 6.5.1.2 are met. 
4th occurrence: Permanently discontinue dabrafenib and trametinib

Grade 4: Life-threatening consequences; dialysis indicated	
 Consult with specialist and recommend renal biopsy. Promote hydration and cessation of nephrotoxic drugs. 	
 Permanently discontinue dabrafenib and trametinib.

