Grade 3: Moist desquamation, ulceration, blistering or severe pain of the hands or feet, or severe discomfort that causes the subject to be unable to work or perform activities of daily living	
 Recommend topical therapy for symptomatic relief 	
1st occurrence:
 
 Interrupt dabrafenib and trametinib until toxicity resolves to ≤ Grade 1 or baseline. Once recovered, reduce dabrafenib and trametinib to the next dose level per Table 6-5. Re-escalation of the subject's dose is recommended if criteria in Section 6.5.1.2 are met 
2nd occurrence:
 
 Interrupt dabrafenib and trametinib until toxicity recovers to ≤ Grade 1 or baseline. Once recovered, reduce dabrafenib and trametinib to the next dose level per Table 6-5. Re-escalation of the subject's dose is recommended if criteria in Section 6.5.1.2 are met 
3rd occurrence:
 
 Discontinue dabrafenib and trametinib.

6.5.1.3.9 Mandatory dose modifications and recommended clinical management guidelines for hematological adverse events

Guidelines for dose modification for hematologic adverse events suspected to be related to study treatment by the investigator are provided in [Table 6-13](#).

Table 6-13 Mandatory dose modifications and recommended clinical management guidelines for hematological adverse events

Hematologic suspected AEs (NCI-CTCAE v4.03)		
Grade	Recommended adverse event management guidelines	Mandatory dose modification requirements
Neutropenia		
Grade 1, 2	NA	
 Continue dabrafenib and trametinib at the same dose.

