Grade 3, 4	
 Monitor blood test more frequently (every 7 days for Grade 3, and 3-5 days for Grade 4). 	
1st occurrence:
 
 Interrupt dabrafenib and trametinib until toxicity recovers to \leq Grade 2 or baseline. Reduce dabrafenib and trametinib to the next dose level per Table 6-5. Re-escalation of the subject's dose is recommended if criteria in Section 6.5.1.2 are met 
2nd occurrence:
 
 Interrupt dabrafenib and trametinib until toxicity recovers to \leq Grade 2 or baseline. Reduce dabrafenib and trametinib at the next dose level per Table 6-5. Re-escalation of the subject's dose is recommended if criteria in Section 6.5.1.2 are met 
3rd occurrence:
 
 Interrupt dabrafenib and trametinib until toxicity recovers to \leq Grade 2 or baseline. Once recovered, reduce dabrafenib and trametinib to the next dose level per Table 6-5. Re-escalation of the subject's dose is recommended if criteria in Section 6.5.1.2 are met 
4th occurrence:
 
 Permanently discontinue dabrafenib and trametinib
Febrile Neutropenia	
 Apply Institutional guidelines 	
 Follow modification guide for neutropenia Grade 4 (above).
Thrombocytopenia		
Grade 1, 2, 3 without clinically significant bleeding	
 Grade 3: monitor blood test more frequently (every 7 days) 	
 Continue dabrafenib and trametinib at the same dose.

Hematologic suspected AEs (NCI-CTCAE v4.03)		
Grade	Recommended adverse event management guidelines	Mandatory dose modification requirements

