Grade 3 with clinically significant bleeding Grade 4	
 Grade 3: monitoring blood test more frequently (every 3-5 days) 	
1st occurrence:
 
 Interrupt dabrafenib and trametinib until toxicity resolves to ≤ Grade 2 or baseline. Restart dabrafenib and trametinib at same dose. 
2nd occurrence:
 
 Interrupt dabrafenib and trametinib until toxicity resolves to ≤ Grade 2 or baseline. Restart dabrafenib and trametinib at the next lower dose per Table 6-5. Re-escalation of the subject's dose is recommended if criteria in Section 6.5.1.2 are met 
3rd occurrence:
 
 Interrupt dabrafenib and trametinib until toxicity resolves to ≤ Grade 2 or baseline. Restart dabrafenib and trametinib at another lower dose per Table 6-5. Re-escalation of the subject's dose is recommended if criteria in Section 6.5.1.2 are met 
4th occurrence:
 
 Interrupt dabrafenib and trametinib until toxicity resolves to ≤ Grade 2 or baseline. Permanently discontinue dabrafenib and trametinib.

6.5.1.3.10 Mandatory dose modifications and recommended clinical management guidelines for non-hematological adverse events

Guidelines for dose modification for non-hematologic adverse events suspected to be related to study treatment by the investigator are provided in [Table 6-14](#).

Table 6-14 Mandatory dose modifications and recommended clinical management guidelines for non-hematological adverse events

Non-Hematologic AEs (except Grade 2 alopecia, Grade 2 fatigue) (NCI-CTCAE v4.03)		
Grade	Recommended adverse event management guidelines	Mandatory dose modification requirements
Grade 1-2 tolerable	
 Monitor closely. Provide supportive care according to institutional standards. 	
 Continue, dabrafenib and trametinib at the same dose.

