Grade 1 ^a	
 Consult ophthalmologist within 7 days of onset 	
 If dilated fundus examination cannot be performed within 7 days of onset, interrupt trametinib until RPED and RVO can be excluded by retina specialist/ophthalmologist. Continue dabrafenib. If RPED and RVO excluded, continue (or restart) trametinib at the same dose level. If RPED suspected or diagnosed: see RPED dose modification in Table 6-19; report as SAE if diagnosed. If RVO diagnosed: Permanently discontinue trametinib and report as SAE.
Grade 2 and Grade 3	
 Consult ophthalmologist immediately, perform ophthalmological evaluation within 24 hours. 	
 Interrupt trametinib. Dabrafenib may be continued at the same dose ^b. If RPED and RVO excluded, restart trametinib at the same dose level. If RPED diagnosed, see RPED dose modification in Table 6-19; report as SAE. If RVO diagnosed: Permanently discontinue trametinib and report as SAE.
Grade 4	
 Consult ophthalmologist immediately, perform ophthalmological evaluation within 24 hours. 	
 Interrupt trametinib. Dabrafenib may be continued at the same dose ^b. If RPED and RVO excluded, should consider restarting trametinib at same or reduced dose after discussion with study medical monitor. If RVO or RPED diagnosed, permanently discontinue trametinib and report as SAE.

^a. If visual changes are clearly unrelated to study treatment (e.g., allergic conjunctivitis), monitor closely but ophthalmic examination is not required.

^b. Permanently discontinue dabrafenib for ≥ Grade 2 uveitis (including iritis and iridocyclitis) of > 6 weeks duration.

Table 6-19 Mandatory dose modification and recommended clinical management for retinal pigment epithelial detachments (RPED) suspected to be related to trametinib treatment

Retinal pigment epithelial detachments (RPED) CTCAE Version 4.03		
Grade	Recommended adverse event management guidelines	Mandatory dose modification requirements

 Grade 1 (Asymptomatic; clinical or diagnostic observations only) 	
 If RPED worsens follow instructions below. 	
 Continue treatment with retinal evaluation monthly until resolution.

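### Section 6.5.1.2 stops both drugs if a related event is not at Grade 1 or baseline by week 4, Table 6-13 restarts and continues dosing at Grade 2, and the protocol does not say which governs

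*Protocol*

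**What the plan says.** **General rule (Protocol Section 6.5.1.2).** The trigger is a treatment-related event for which both drugs have been interrupted. If that event has not come down to at most "Grade 1 or baseline within 4 weeks, dabrafenib and trametinib must be discontinued". The Glossary defines discontinuation of study treatment as a permanent stop. Section 9.1.1 makes meeting the stopping criteria of Section 6.5.1 a reason for which treatment must end.

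**Exceptions beside the rule.** Section 6.5.1.2 says that for toxicities specific to the combination "both treatments should be simultaneously dose reduced, interrupted or discontinued with the exceptions shown below". The exceptions are uveitis (dabrafenib only) and RVO, RPED and LVEF reduction (trametinib only). They settle which drug is modified. Haematology is not among them.

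**Haematology table (Protocol Section 6.5.1.3.9, Table 6-13).** Its scope is set by the sentence that introduces it ("Guidelines for dose modification for hematologic adverse events suspected to be related to study treatment by the investigator are provided in"), which ends by naming the table. Its dose-modification column is labelled mandatory.

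- Neutropenia Grade 1-2: "Continue dabrafenib and trametinib at the same dose".
- Neutropenia Grade 3-4, first occurrence: hold both drugs until at most "Grade 2 or baseline. Reduce dabrafenib and trametinib to the next dose level". The second and third occurrences use the same recovery level, and the fourth is a permanent stop.
- Febrile neutropenia: handled as Grade 4 neutropenia.
- Thrombocytopenia Grade 3 with clinically significant bleeding, or Grade 4, first occurrence: hold both drugs until at most "Grade 2 or baseline. Restart dabrafenib and trametinib at same dose". The second and third occurrences restart at a lower dose from the same recovery level, and the fourth is a permanent stop.
- Thrombocytopenia Grade 1-2: dosing continues unchanged.

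Table 6-13 sets no time limit on recovery.

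**The concern.** Both instructions are mandatory and both apply to haematologic events judged related to treatment. They use different recovery levels, and only one has a deadline. A site treating a subject as Table 6-13 directs can therefore find at week 4 that the general rule requires both drugs to be stopped for good.

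Two things are at stake. For the subject, the reading decides whether adjuvant treatment continues. For the analysis, the proportion permanently discontinued due to any adverse event by 12 months is a secondary endpoint (Protocol Table 2-1; SAP Section 5.8.1, with an exact confidence interval). If sites resolve the conflict differently, part of that proportion reflects interpretation of the protocol and not tolerability. The same ambiguity makes it unclear which conduct is a protocol deviation, and SAP Section 5.3.1 tabulates deviations.

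**Working it through.** No plan figure needs reproducing. The check sets the two rules side by side and follows a subject through both.

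| | Section 6.5.1.2 | Table 6-13 |
|---|---|---|
| Events | all treatment-related events | related haematologic events |
| Trigger | interruption of both drugs | Grade 3-4 neutropenia; febrile neutropenia; thrombocytopenia Grade 3 with bleeding or Grade 4 (each interrupts both drugs) |
| Recovery level | Grade 1 or less, or baseline | Grade 2 or less, or baseline |
| Time limit | 4 weeks | none |
| If the level is met | no stop required | restart, occurrences 1 to 3 |
| If the level is not met | both drugs discontinued | interruption continues |

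**Worked case.** A subject with a normal baseline has a first Grade 3 neutropenia and both drugs are interrupted. The count reaches Grade 2 at week 2 and is still Grade 2 at week 4.

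- Table 6-13: restart at week 2 at the next dose level. At week 4 the Grade 1-2 row says to continue.
- Section 6.5.1.2: at week 4 the event is neither at Grade 1 or less nor at baseline, so both drugs must be discontinued.

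Both cannot be followed at week 4. The thrombocytopenia rows give the same result.

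**Where the rules agree or do not collide.**

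- Grade 1 or less, or baseline, reached within 4 weeks: no conflict. A subject whose baseline is Grade 2 falls here, because both rules accept return to baseline.
- Fourth occurrence: Table 6-13 itself stops treatment permanently.
- Still Grade 3 or worse at week 4: the table only prolongs the hold and does not direct dosing, so this case is not counted as part of the conflict.

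The conflict is confined to occurrences 1 to 3 that have improved to Grade 2 but are above Grade 1 and above baseline at week 4.

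**Search for a tie-breaker.** Neither passage states precedence. The listed exceptions omit haematology. Other tables carry the 4-week recovery limit themselves: Table 6-7 (liver), Table 6-9 (rash), Table 6-10 (pneumonitis) and Table 6-17 (diarrhoea). Table 6-13 has neither the limit nor an exemption from it, so a reader cannot tell whether haematology was exempted on purpose.

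**Effect per subject on the secondary endpoint.** With the SAP's 556 subjects, each subject whose status turns on the site's reading moves the proportion by 1/556 = 0.0018, or about 0.18 percentage points.

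**The case against.** The strongest reply is that the two rules can be applied in sequence: restart at Grade 2 as the table directs, then stop if Grade 1 or baseline is not reached by week 4. Section 6.5.1.2 does not forbid a restart at Grade 2. It is also arguable that its clock concerns only failure to recover while dosing is held. The first part is right and limits the point: a Grade 2 restart is not in itself a breach. But stopping at week 4 still overrides the table's mandatory instruction to continue at Grade 2, and the text does not say that the clock ends at restart.

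A second reply is that the layout favours the specific table. Section 6.5.1.2 points to Table 6-6 for the detailed requirements, and Table 6-6 sends haematologic events to Table 6-13, with a separate general row for Table 6-11. That makes precedence of the table a reasonable guess. It is routing, not an override, and Section 9.1.1 makes the stopping criteria in Section 6.5.1 binding without distinction.

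A third reply concerns reach, and it largely stands. The most frequent Grade 3/4 events listed for the adjuvant historical study in Section 1.1.1.6 (hypertension 6%, pyrexia 5%, fatigue 4%, elevated ALT 4%) do not include neutropenia or thrombocytopenia. The affected endpoint is descriptive, with no threshold. On the other side, neutropenia is an event of special interest for the combination (Table 10-1), and Section 1.1.1.3 reports a higher incidence than on either monotherapy in metastatic disease.

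Three stronger readings are not supported:

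- **Uveitis.** A reader might see a conflict between the 4-week rule and the limit of more than 6 weeks in Table 6-18. The general rule is triggered only when both drugs are interrupted. Section 6.5.1.2 lists uveitis as a dabrafenib-only modification, and Section 6.5.1.3.15 requires no change to trametinib.
- **Thrombocytopenia up to Grade 3 without bleeding.** Dosing continues without interruption, so the general rule is never triggered.
- **A count of affected subjects.** The documents give neither the adjuvant rate of these events nor the share still at Grade 2 at week 4.

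**Conclusion.** The contradiction is real and narrow. For a related haematologic event that led to interruption of both drugs, improved to Grade 2, and is not at Grade 1 or baseline by week 4, Section 6.5.1.2 and Table 6-13 give opposite mandatory instructions on permanent discontinuation, with no stated precedence. This rests on the general rule covering haematologic events, which its wording does, and on the 4-week clock continuing after a restart, which the text does not exclude.

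The number of subjects affected cannot be derived. A reader might infer that the primary result is at risk. The primary endpoint counts pyrexia outcomes only, so it is not directly affected. The exposed quantity is the proportion permanently discontinued due to any adverse event by 12 months.

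**What to change.** Reconcile Section 6.5.1.2 with Table 6-13. Either state in Section 6.5.1.2 whether an event-specific recovery grade overrides the general 4-week rule, or align the two passages on recovery level and time limit. If the general rule is meant to apply, say whether its clock continues after a restart. The sponsor's medical team decides the rule; this review takes no position on which is clinically right.

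The cost is one or two sentences in a protocol clarification or site letter, with no new assessments. This helps only while subjects are on treatment. Once treatment has ended, as the SAP's planned cut-off for the primary analysis implies, the remaining step is to state in the study report which reading was intended and to identify haematologic discontinuations of this kind from the adverse event and dosing listings already planned.
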